# VISIT 3 (1.5 hrs)

This visit starts the official glycaemic baseline data collection point. This constitutes 21 days of blinded continuous glucose monitoring. The study participant will attend the research facility to have a 4th generation sensor inserted and GST3C minilink attached. Subjects will receive the following instruction:

- i. Expectations of minimum 4x/day glucose testing using CONTOUR® NEXT LINK 2.4 glucometer. Participants will be instructed that an addition to any glucose values recorded on their usual glucometer, they will need 4x additional values (can be taken concurrently) taken on a CONTOUR® NEXT LINK 2.4 glucometer which will be issued to them at this visit.
- ii. Instructed to collect prospective data over the following 21-28 days and record into the diary:
  - 1. Symptomatic hypoglycaemia requiring carbohydrate rescue
  - 2. Time off work / school (including parents)
  - 3. Insulin dosing (MDI participants)
- iii. Instruction on the logbook, with respect to identifying contacts (investigative staff) for trouble shooting and technical issues for the following 21-28 days.

At this visit, all participants will be issued with the following:

- i. Participant logbook
- ii. CONTOUR® NEXT LINK 2.4 glucometer

VISIT 4 and Visit 5 (30 minutes each)

7 days after sensor insertion, participants will return to download the first week of CGM data. The CONTOUR® NEXT LINK 2.4 glucometer will be uploaded. A new sensor will be inserted and a fresh GST3C attached. The logbook will be revised, and participants reminded to keep records accurate and up to date. This is repeated in another 7 days. If there is insufficient CGM data collected by visit 5 (>70% of of each 7 day period having CGM recordings),or due to a technical reason for the CGM data not being available for the minimum amount, participants will be offered additional CGM collection to meet the requirement of the protocol.

HCL outpatient Version Number:6.0 Version Date:15/07/2019

#### VISIT 6 (3 hours)

This visit is the randomization visit, and allocation is dependent on the stratifications listed previously.

The following data will be collected prior to randomization:

- Auxological i.
- a) Height, weight, BMI.
- ii. Diabetes clinical
- a) Blood pressure
- b) Previous 7 days' total daily dose insulin (including basal and bolus proportions)
- c) Carbohydrate ratios and insulin sensitivity factor
- d) Logbook will be collected. Symptomatic hypoglycaemia requiring carbohydrate rescue in the previous 14 days and time off work or school will be collected from the participant logbook
- iii) Biomarkers

A detailed description of sample preparation for biomarkers is found in appendix 15.9. 12mL of blood and 50mL of urine will be collected.

- a) Cell Adhesion Molecules (CAM)S
- b) Soluble vascular cell adhesion molecules sVCAM
- c) Soluble intercellular adhesion molecules sICAM
- d) s-e Selectin
- e) Oxidized Low density lipoprotein
- f) Myeloperoxidase.
- g) MicroRNA signatures for arterial, renal and retinal complications
- h) Telomerase
- i) DNA methylation/acetylation
- j) Glycomark
- k) Isoprostanes and proteomics
- 1) Clotting profile

Participant randomization will occur at the completion of the tasks above (for details on randomization process see section 7.3.1). Once randomized a date will be booked for entry into the study arm (visit 7), which should be no longer than 2 weeks after visit 6.

VISIT 7 (visit schedule dependent on randomization and baseline therapy)

#### i. THOSE RANDOMIZED TO STANDARD THERAPY:

**MDI regimen:** Participants will be issued a new logbook and instructed to prospectively to fill in interruptions from work/school.

**CSII:** Participants will be issued a new logbook and instructed to prospectively to fill in interruptions from work/school and document any insulin pump technical issues (insulin infusion site failures).

Investigators will log all time spent training and communication with participant.

#### ii. THOSE RANDOMIZED TO HCL THERAPY:

MDI to HCL: Participants will require general pump education, and standard insulin pump therapy stabilization prior to HCL initiation.

Visit 7A: DNE initial pump training (8hours) including programming the pump, demonstrating line insertion

Participant will be issued the MinimedTM 670G insulin pump and participant user guide.

Visit 7B: Within the next three days, return to observe line change if required and participant is unconfident. Weekly phone/email contact to support pump transition for the following 2 weeks. Participants will upload their pump weekly. Communication can be more often – as per clinical need, and logged by investigators.

Visit 7C: 2 weeks after pump start: Initiate CGM (2 hours), with training on CGM use, alarm settings, training on CGM insertion and changing sensor. Initial low and high alarms will be set at 4.0mmol/L and 15mmol/L respectively, although these can be changed according to individual preference. Rate alarms, suspend on low and suspend before low functions will not be activated.

At this visit participants will be issued with 4th generation sensors and the GST3C transmitter, as well as CGM user guide and instructions for contact persons to assist any troubleshooting

Visit 7D: 2 – 4 weeks post pump start and stabilization, and a minimum of 3 days CGM, face to face for instruction on how to operate HCL, and HCL initiated (2 hours). There will be opportunity for those unfamiliar with CGM use to practice a sensor change with supervision. Upon HCL initiation, participants will be instructed to avoid excessive exercise for 48hrs while the algorithm adapts.

Further, at this point participants will be issued a new logbook and instructed to prospectively to fill in interruptions from work/school and document any insulin pump technical issues (insulin infusion site failures, sensor changes, unplanned exit from HCL). Participants will subsequently have weekly communication via phone call or email for support for the following 4 weeks, and upload their pump weekly. Investigators will log all time spent training and communication with participant. Communication can be more often – as per clinical need, and logged.

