#### 5. Health-economic

Report the health economic impact of the MiniMed™ 670G Insulin Pump Hybrid Closed Loop System Vs standard therapy (MDI and CSII). The following data points will be used as part of the economic analysis:

- i. QALYs calculated from the EQ-5D
- ii. Hypoglycaemic events and HbA1c
- iii. Participant reporting on work interruption
- iv. Investigator reporting time spent on training, education and support, by the type of health professional resource used
- v. Diabetes management consumables (glucose strips, ketone strips, batteries, sensors, site dressings, lancets, needles, insulin).

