End of study assessments	Visit 16:							
	i) Auxological							
	a. Height							
	b. Weight							
	ii) CGM glycaemic data and all secondary glycaemic							
	measures							

	
 
iii) Seated blood pressure (average of 2 readings)
 
iv) Total daily dose, basal and bolus proportion, carbohydrate ratio and insulin sensitivity factor
 
v) Psychological assessments (age specific)
 
vi) Biomarkers
 
vii) Semi structured interview
 
						
Continuous Assessments	Technology interactions/human factors (repeated sampling)						
	through mobile phone app.  ii. Investigator time spent training (carbohydrate counting, HCL training) and support.  iii. Time off work and school  iv. Consumable use (sensors, pump sites)  v. Health care providers expectations and experiences (repeated sampling through mobile phone app)						
Procedures for safety	Safety measures will be recorded including ketone levels.						
monitoring during trial	Establishment of a data safety and monitoring board (DSMB) to scrutinise conduct of the study and study team and to monitor safety data arising from the study in order to determine if stopping the trial is required. Refer appendix 15.12						
Criteria for withdrawal of participants on safety grounds	A subject may terminate participation in the study at any time without necessarily giving a reason and without any personal disadvantage. An investigator can stop the participation of a subject after consideration of the benefit/risk ratio. Possible reasons are:  1. Serious Adverse Events 2. Inability to meet study requirements (e.g. regularly upload pump history to computer) 3. Technical grounds 4. Early termination of the study at the request of the steering committee or data safety monitoring board						

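### Participants' logging of work and school interruption starts at Visit 7 for controls but only at closed-loop initiation for the HCL arm, so the HCL start-up period has no such record

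*Protocol*

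**What the plan says.** At Visit 6, before randomisation, the baseline logbook is returned: "Logbook will be collected". Entry into the allocated arm is Visit 7, "which should be no longer than 2 weeks after visit 6".

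For the standard therapy arm, on MDI or CSII, the Visit 7 text reads: "Participants will be issued a new logbook and instructed to prospectively to fill in interruptions from work/school". CSII controls also note infusion site failures from then on.

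For the HCL arm, Visit 7 is split into parts. Ex-MDI participants start with "DNE initial pump training (8hours) including programming the pump, demonstrating line insertion" at 7A, may return at 7B, and have 2 hours of CGM training at 7C, two weeks after pump start. They begin closed loop at 7D, timed as "2 – 4 weeks post pump start and stabilization, and a minimum of 3 days CGM". Only in the 7D text does the logbook appear: "Further, at this point participants will be issued a new logbook and instructed to prospectively to fill in interruptions from work/school". Ex-CSII participants train for 2 to 4 hours at 7A and receive the logbook at 7B, after 3 to 7 days of CGM. In both cases the HCL logbook also covers infusion site failures, sensor changes and unplanned exits.

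The synopsis lists "Time off work and school" under Continuous Assessments. The health-economic endpoint names "Participant reporting on work interruption" as one of five data points. Investigator time on training and support is another.

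**The concern.** Work and school interruption is a participant-reported outcome that will be compared between randomised arms, yet recording starts at an arm-dependent point. The unrecorded stretch is also not an ordinary slice of follow-up. It is when HCL participants attend pump and CGM training and, if they come from injections, make their first infusion-set changes. Controls have no equivalent start-up burden and are already recording.

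Cost-effectiveness is a stated hypothesis of the trial (synopsis, hypothesis 5). If the visit text is followed as written, one input to that comparison is measured differently by arm, and a diary that was never issued cannot be filled in later. The visit text also does not deliver what the synopsis promises for the HCL arm.

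**Working it through.** The protocol gives no figure of its own to reproduce. The check sets the visit texts side by side, expresses the gap as a share of follow-up, and illustrates its possible effect.

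**1. Start of logging, with follow-up taken as 26 × 7 = 182 days from Visit 7/7A**

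| Group | Logbook issued | Gap after Visit 7/7A | Share of 182 days |
|---|---|---|---|
| Control, MDI or CSII | Visit 7 | 0 days | 0% |
| HCL, ex-MDI | Visit 7D | 14–28 days | 14/182 = 7.7% to 28/182 = 15.4% |
| HCL, ex-CSII | Visit 7B | 3–7 days | 3/182 = 1.6% to 7/182 = 3.8% |

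If 7C falls at two weeks and three days of CGM must follow, the shortest ex-MDI gap is 14 + 3 = 17 days, or 9.3%. Later visits do not compensate: Visits 13 to 15 are timed from Visit 7a, not from closed-loop initiation. The interval of up to two weeks between Visits 6 and 7 applies to both arms and is not differential.

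**2. Arm-level average**

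The MDI share s of the HCL arm is not stated. The mean gap is s × (14 to 28) + (1 − s) × (3 to 7) days:

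- s = 25%: 5.75 to 12.25 days, 3.2% to 6.7% of 26 weeks
- s = 50%: 8.5 to 17.5 days, 4.7% to 9.6%
- s = 75%: 11.25 to 22.75 days, 6.2% to 12.5%

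**3. Training inside the ex-MDI gap**

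8 h (7A) + 2 h (7C) = 10 h, plus an optional 7B. The 2 h at 7D fall on the visit at which the logbook is issued and are not counted. If all 10 h fell in work or school time, which the protocol does not say, that would be 10/8 = 1.25 eight-hour days.

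**4. Illustrative effect on recorded loss, ex-MDI**

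Let w be the weeks without a logbook (2 to 4), and m the assumed ratio of weekly loss during start-up to weekly loss afterwards. With later loss set to 1 per week:

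- true total = (26 − w) + m × w; recorded total = 26 − w
- undercount of the total = m × w / true total
- bias of the rate per logged week = 26 / true total − 1

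| m | Undercount of total, w = 2 to 4 | Bias per logged week, w = 2 to 4 |
|---|---|---|
| 0.5 | 4.0% to 8.3% | +4.0% to +8.3% |
| 1 | 7.7% to 15.4% | 0% |
| 2 | 14.3% to 26.7% | −7.1% to −13.3% |
| 3 | 20.0% to 35.3% | −13.3% to −23.5% |

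For example, with m = 2 and w = 2 the true total is 24 + 4 = 28, the undercount is 4/28 = 14.3%, and the rate bias is 26/28 − 1 = −7.1%. Totals are understated at every positive m. The rate can err in either direction.

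**5. Other sources**

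The weekly app questions in appendix 15.9 do not ask about missed work or school. No other instrument is named for it.

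**The case against.** The strongest reply is that the start-up effort is not lost. Investigators log training and communication time in both arms, and that time is an economic input. This stands for staff time. It does not show whether a participant or parent missed work or school, which the protocol lists as a separate input.

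A second reply is that the synopsis calls the assessment continuous, so sites may record it throughout. That makes this an inconsistency to reconcile rather than proven loss of data, but the operational text is what sites will follow.

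Some stronger readings are tempting, and the protocol does not support them:

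- A reader might infer that the visit table also contradicts the visit text, because it marks logbook recording at Visit 7. It does not. Visits 7A to 7D are all Visit 7, and the table's footnote allows the requirement to vary by allocation.
- A reader might infer that the economic comparison is shown to favour HCL. Work interruption is one of five inputs, the economic analysis is described only as separate, and per logged week the bias can be nil or run against HCL.
- A reader might infer that missing line failures bias the comparison between arms. They are a 670G performance parameter reported descriptively, and not a listed economic input.

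It is also fair that the gap is short for ex-CSII participants, and that the primary endpoint comes from CGM and does not depend on the logbook.

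**Conclusion.** The point holds as a differential start of recording. Followed as written, the HCL arm has no participant record of work or school loss for 14 to 28 days (ex-MDI) or 3 to 7 days (ex-CSII) during which controls are recording, and this conflicts with the synopsis. Recorded HCL productivity loss may be understated. That direction follows for uncorrected totals, provided any loss occurs in the gap. For rates per logged week it holds only if loss during start-up exceeds later loss, which is plausible given the scheduled sessions but not established.

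The lengths of the gap come directly from the protocol. The size of the bias does not: it rests on the assumed ratio m, the unstated MDI share, and an economic method that is not shown. Early line failures may be undercounted in the device report, which matters for that description only. The issue is limited in reach, but worth correcting because the remedy is nearly free and the data cannot be recovered afterwards.

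**What to change.** Issue the new logbook at the same point in both arms: preferably at Visit 6, when the baseline one is collected, and at the latest at Visit 7 for controls and 7A for HCL. Visit 6 would also close the interval before Visit 7 that both arms share.

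Have work and school interruptions recorded from the day of issue, and pump technical issues from the first pump day at 7A. Remove from the 7D and 7B texts the words that tie the logbook to closed-loop initiation, so that they agree with the synopsis. State that work and school loss is counted from the same origin in both arms.

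The cost is a wording amendment and earlier handover of an existing logbook, with no new instrument or visit. The downside for the sponsor is that HCL costs may look slightly less favourable.

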# **CSII to HCL:** Participant 670G, CGM education and HCL training.

Visit 7A: Participants will be trained on how to use the Medtronic 670G insulin pump. They will also be instructed on how to link CGM on the Medtronic 670G pump (allow 2-4 hours) and issued with Enlite III and the GST3C transmitter, as well as CGM user guide. Initial low and high alarms will be set at 4.0mmol/L and 15mmol/L respectively, although these can be changed according to individual preference. Rate alarms, suspend on low and suspend before low functions will not be activated.

Visit 7B: Once CGM data has been established for a minimum of 3 days, and maximum 7 days, participant returns for face to face instruction on HCL use and initiation. During this visit the sensor will be replaced, to demonstrate sensor warm up and HCL initiation, and provide an opportunity for those unfamiliar with CGM use to practice a sensor change with supervision. Upon HCL initiation, participants will be instructed to avoid excessive exercise for 48hrs while the algorithm adapts.

Further, at this point participants will be issued a new logbook and instructed to prospectively to fill in interruptions from work/school and document any insulin pump technical issues (insulin infusion site failures, sensor changes, unplanned exit from HCL). Participants will be issued glucose testing strips for the already issued CONTOUR® NEXT LINK 2.4 glucometer - enough to last 12 weeks.

Participants will subsequently have weekly communication via phone call or email for support for the following 4 weeks, and upload their pump weekly. Investigators will log all time spent training and communication with participant. Communication can be more often – as per clinical need, and logged.

VISIT 8: (4 weeks from Visit 7 if randomised to control)) (If randomized to HCL group, 4 weeks from Visit 7d)

#### THOSE RANDOMIZED TO **STANDARD THERAPY**

Face to face meeting (1hr). Check logbook is being filled out. Revise CSII settings and MDI if necessary. If on CSII upload the insulin pump. Schedule visit 9 and 10.

#### 7.4.2 THOSE RANDOMIZED TO HCL

Face to face meeting (1hr). Check logbook is being filled out. Upload insulin pump, and revise insulin sensitivity and carbohydrate ratio. Schedule visit 9.

VISIT 9 (11 weeks from Visit 7) 30 minutes)

#### i. THOSE RANDOMIZED TO STANDARD THERAPY

The study participant will attend the research facility to have a 4th generation sensor inserted andGST3C transmitter attached. Subjects will receive the following instruction:

- a) Expectations of minimum 4x/day glucose testing using CONTOUR® NEXT LINK 2.4 glucometer.
- b) Instructed to collect prospective data over the following 2 weeks and record into the logbook:
  - 1. Symptomatic hypoglycaemia requiring carbohydrate rescue
  - 2. Time off work / school
  - 3. Insulin dosing (MDI participants)

## ii. THOSE RANDOMIZED TO HCL

Participants will have a 2nd, 4th generation sensor inserted andGST3C transmitter attached. Subjects will receive the following instruction:

- a) Expectations of minimum 4x/day glucose testing using CONTOUR® NEXT LINK 2.4 glucometer.
- b) Instructed to collect prospective data over the following 2 weeks and record into the logbook:
  - 1. Symptomatic hypoglycaemia requiring carbohydrate rescue
  - 2. Time off work / school

VISIT 10 (12 weeks from Visit 7), 30 minutes).

7 days after sensor insertion, participants will return to download the first week of CGM data. The CONTOUR® NEXT LINK 2.4 glucometer will be uploaded. A new sensor will be inserted and a fresh GST3C attached. The logbook will be revised, and participants reminded to keep records accurate and up to date.

VISIT 11: (13weeks since Visit 7), 4 hours).

All participants will have a clinical review of insulin settings (MDI, CSII and HCL) and refresher on carbohydrate counting. An additional CGM week and visit will be required if there is <70% of available CGM time available from the upload.

The following data will be collected at the midpoint:

- i. Auxological
  - a. Height, weight, BMI
- ii. Glycaemic:
  - a. CGM uploaded for standard therapy on MDI and CSII
  - b. 670G uploaded for HCL participants
- iii. Diabetes clinical
  - a. HbA1c
  - b. Blood pressure (average of 2 readings)
  - c. Previous 7 days' total daily dose insulin (basal and bolus proportions for participants on insulin pump therapy)
  - d. Carbohydrate ratios and insulin sensitivity
  - e. Symptomatic hypoglycaemia requiring carbohydrate rescue in the previous 14 days from participant logbook.
- Psychological assessments: iv.
  - a. Fear of hypoglycaemia: Hypoglycaemic Fear Survey-II Worry scale: 17-<25years. Children's Hypoglycaemia Fear survey 12 – 17 years.
  - b. Hypoglycaemia Awareness: Hypoglycaemia Awareness Scale (Gold Score) (all ages)
  - c. Anxiety: State-Trait Anxiety Inventory (Child version for 12-15yrs, adult version >16-<25vrs).
  - d. Impact and Satisfaction: The Diabetes Treatment Satisfaction Questionnaire status and change version (16 - <25 years)
  - e. Quality of Life: 12-<25 years: EQ-5D-Y,
  - f. **Diabetes specific quality of life**: PedsQL Child version (12 years), Adolescent version (13 – 18 years) and young adult version (18 – <25 years).
  - g. **Diabetes distress:** *Problem Areas in Diabetes (Teen version for 12 17 years,*  $standard\ version \ge 17 - <25 yrs)$

Participants will be issued a third logbook for the second half of the study documenting symptomatic hypoglycaemia requiring carbohydrate rescue and interruptions from work/school, and document any insulin pump technical issues (insulin infusion site failures, sensor changes, unplanned exit from HCL).

Participants will be issued with enough consumables for the remainder of the study.

VISIT 12: week 23 from Visit 7. (30 minutes)

# THOSE RANDOMIZED TO STANDARD THERAPY

The study participant will attend the research facility to have a 4th generation sensor inserted and GST3C transmitter attached. Subjects will receive the following instruction:

- A) Expectations of minimum 4x/day glucose testing using CONTOUR® NEXT LINK 2.4 glucometer.
- b) Instructed to collect prospective data over the following 3 weeks and record into the logbook:
  - 1. Symptomatic hypoglycemia requiring carbohydrate rescue
  - 2. Time off work / school
  - 3. Insulin dosing (MDI participants)

## iii. THOSE RANDOMIZED TO HCL

Participants will have a 4th generation sensor inserted andGST3C transmitter attached. Subjects will receive the following instruction:

- a) Expectations of minimum 4x/day glucose testing using CONTOUR® NEXT LINK 2.4 glucometer.
- b) Instructed to collect prospective data over the following 2 weeks and record into the logbook:
  - 1. Symptomatic hypoglycaemia requiring carbohydrate rescue
  - 2. Time off work / school

VISIT 13, 14 and 15 (24 and 25 and 26 weeks from Visit 7a, 30 minutes each). Note that visit 16 will occur on the same day as visit 15 if sufficient CGM data has been captured.

7 days after sensor insertion, participants will return to download the previous 7 days of CGM data. The CONTOUR® NEXT LINK 2.4 glucometer will be uploaded. A new sensor will be inserted and a fresh GST3C attached. The logbook will be revised, and participants reminded to keep records accurate and up to date. This is repeated for visit 13, 14 and 15 supplemental as required. If there is insufficient CGM data collected (>70% of of each 7 day period having CGM recordings),or due to a technical reason for the CGM data not being available for the minimum amount, participants will be offered additional CGM collection to meet the requirement of the protocol.

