# **6.3 Study Endpoints**

## **6.3.1 Primary Endpoint:**

The % time sensor glucose level is in target range (3.9–10 mmol/L) during HCL insulin delivery vs standard therapy (MDI and CSII), measured 23-26 weeks post-randomisation.

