## VISIT 16: Week 26 post randomization (**study end,** 4 hours)

The following data will be collected at the endpoint:

- i. Auxological
  - a. Height, weight, BMI.
- ii. Glycaemic:
  - a. CGM uploaded for those standard therapy (MDI and CSII)
  - b. 670G uploaded for HCL participants
- iii. Diabetes clinical
  - a. HbA1c
  - b. Blood pressure (average of 2 readings)
  - c. Previous 7 days' total daily dose insulin (basal and bolus proportions for participants on insulin pump therapy)
  - d. Carbohydrate ratios and insulin sensitivity
  - e. Symptomatic hypoglycaemia requiring carbohydrate rescue in the previous 21 days from participant logbook.
- iv. Psychological assessments:
  - a. **Fear of hypoglycaemia**: Hypoglycaemic Fear Survey-II Worry scale: 17-<25years. Children's Hypoglycaemia Fear survey 12 – 17 years.
  - b. **Hypoglycaemia Awareness**: *Hypoglycaemia Awareness Scale (Gold Score) (all ages)*
  - c. **Anxiety**: State-Trait Anxiety Inventory (Child version for 12-15yrs, adult version ≥16-<25yrs).
  - d. **Impact and Satisfaction**: The Diabetes Treatment Satisfaction Questionnaire status and change version (16 <25 years)
  - e. Quality of Life: 12-<25 years: EO-5D-Y,
  - f. **Diabetes specific quality of life**:  $PedsQL Child \ version \ (12 \ years) \ Adolescent \ version \ (13 18 \ years) \ and \ young \ adult \ version \ (18 <25 \ years).$

Page 32 of 85

- g. **Diabetes distress:** Problem Areas in Diabetes (Teen version for 12 17 years, standard version  $\geq 17$ -<25yrs,
- h. Participant reported outcome for Automated Delivery system: INSPIRE Questionnaires: baseline and post-assessment versions Child version (12 year olds), Adolescent version (13-18) and adult version(18-25)
- **Semi structure interview** (all ages)

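### At Visit 12 controls are told to log hypoglycaemia and time off for 3 weeks but HCL participants for 2, although Visit 16 reads back 21 days of logged hypoglycaemia in both arms

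*Protocol*

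**What the plan says.** Section 7.4 (Visit schedule) sets the logging instruction separately for each arm at Visit 12.

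- Standard therapy: "Instructed to collect prospective data over the following 3 weeks and record into the logbook".
- HCL: "Instructed to collect prospective data over the following 2 weeks and record into the logbook".

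Both lists contain symptomatic hypoglycaemia needing carbohydrate rescue and time off work or school. The control list adds insulin dosing for MDI participants.

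Visit 16 then collects, with no distinction by arm: "Symptomatic hypoglycaemia requiring carbohydrate rescue in the previous 21 days from participant logbook".

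Other text bears on how long HCL participants record:

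- Visit 11, both arms: "Participants will be issued a third logbook for the second half of the study documenting symptomatic hypoglycaemia requiring carbohydrate rescue and interruptions from work/school".
- Visits 13, 14 and 15 (weeks 24, 25 and 26), both arms: "The logbook will be revised, and participants reminded to keep records accurate and up to date".
- Visit 7, at the start of HCL use: participants are to log work and school interruptions prospectively and "document any insulin pump technical issues (insulin infusion site failures, sensor changes, unplanned exit from HCL"). No end date is given.
- The schedule table marks logbook data as recorded from Visit 12 through Visit 16.

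Section 7.3 plans incidence rates, and where appropriate Poisson or negative binomial models, for moderate hypoglycaemia taken from the participant log. Section 6.3 lists hypoglycaemic events and work interruption among the inputs to the economic analysis.

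**The concern.** The two arms are in the same three-week sensor block, yet one is told to keep the log for the whole block and the other for two thirds of it. Under-recording shared by both arms would largely cancel in a comparison of rates. Under-recording caused by an instruction given to one arm only does not cancel, and here it runs in favour of HCL. Participants know their treatment and the outcome is self-reported, so identical recording instructions matter more than usual.

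The analysis text does not remove the problem. Section 7.3 does not state the person-time for the log-based rates, while Visit 16 fixes one 21-day window for both arms. If that window becomes the denominator, days on which an HCL participant has stopped logging are counted as days without an event. Third-week entries that were never made cannot be recovered once the logbooks are returned.

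**Working it through.** **Inputs.** The Visit 12 instruction is 3 weeks for controls and 2 weeks for HCL. The Visit 16 extraction is 21 days in both arms. The true event rate is not given; it is assumed equal in the two arms and constant over the block, so it cancels from the ratio.

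**Step 1: which instruction matches the extraction.**

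- Control: 3 x 7 = 21 days, which agrees with Visit 16.
- HCL: 2 x 7 = 14 days, which does not.

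**Step 2: size of the under-count with a common 21-day denominator.** Let f be the share of third-week events that the HCL arm still logs. At equal true rates the expected HCL-to-control ratio of logged events is (2 + f)/3, and the shortfall is 1 - (2 + f)/3.

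| f | Ratio | Shortfall |
|---|---|---|
| 0 | 0.667 | 33.3% |
| 0.25 | 0.750 | 25.0% |
| 0.50 | 0.833 | 16.7% |
| 0.75 | 0.917 | 8.3% |
| 1 | 1.000 | 0% |

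The first row is 14/21, where every HCL participant stops at day 14. The last row is what the Visit 11, Visit 13 to 15 and Visit 16 text prescribes.

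**Step 3: the denominator.** If HCL participants stop at 14 days and each arm's count is divided by its own days of logging, the weekly rate r gives 2r/14 for HCL and 3r/21 for controls. Both equal r/7, so the ratio is 1.00. The bias therefore needs both early stopping and a common 21-day denominator.

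**Step 4: time off work or school.** Visit 16 states no 21-day window for this item, and the synopsis lists it as a continuous assessment. Over the second half of the study (weeks 13 to 26, 13 weeks), losing one week of entries is 1/13 = 7.7%, so the one-third figure does not carry over.

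**Step 5: what the HCL participant is told, in order.** The Visit 11 logbook covers the whole second half. The Visit 12 line says 2 weeks. Reminders follow at weeks 24, 25 and 26. Week 23 + 2 = week 25, so the Visit 14 reminder nominally falls just as the 2-week period would end.

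**Step 6: likely origin.** The 2-week wording is the same as at Visit 9, where both arms have a 2-week sensor block. Text carried over from Visit 9 is plausible but cannot be shown.

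**The case against.** The strongest objection is that the 2-week line is not the operative recording rule. Both arms hold a logbook for the whole second half, all participants are reminded weekly until week 26, the schedule table shows recording through Visit 16, and the 21-day extraction presupposes three weeks of data from everyone. On that reading, sites would carry on logging and nothing would be lost. The person-time for the rates is also a detail that may be settled in an analysis plan not seen here.

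Much of this stands. A reader might infer from Visit 12 alone that HCL participants log for only two weeks and that their log will therefore show a third fewer events. The documents do not support that: the 2-week line is followed by further reminders, and one third is the ceiling of a range that starts at zero. Nor can a false-positive rate be attached to the discrepancy, because the protocol gives no event rate, no between-person variation and no basis for the share who would stop early.

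A reader might also infer that the primary endpoint is at risk because the block coincides with its window, "measured 23-26 weeks post-randomisation". That endpoint comes from sensor glucose. The listed CGM and severe-hypoglycaemia endpoints are likewise not tied to this Visit 12 instruction. Even the link to Section 7.3 involves a step. That section refers to moderate hypoglycaemia, which the protocol does not define, and the visit text asks participants to log symptomatic hypoglycaemia needing carbohydrate rescue. Treating the two as the same is reasonable but is an inference.

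What the objection does not remove is that controls receive consistent instructions and HCL participants receive conflicting ones. A general reminder to keep records up to date does not clearly extend a period stated as two weeks.

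**Conclusion.** The inconsistency is real and is wrong as written: the Visit 12 logging period differs by arm, and the HCL version disagrees with the Visit 16 extraction and with the protocol's other logbook text. Its possible effect is an under-count of logged hypoglycaemia in the HCL arm of 0% to at most 33%, in favour of HCL. The upper end requires all HCL participants to stop at day 14 and 21 days to be used as the denominator; the calculation assumes equal and constant true rates. The effect reaches the participant-log hypoglycaemia rates and possibly the economic inputs, where hypoglycaemic events and work interruption are used. It does not reach the primary endpoint. Because other passages already call for continued recording and the affected outcomes are secondary, this is a minor correction. It is still worth making, because the direction is one-sided and missing entries cannot be restored later.

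**What to change.** Change the HCL instruction at Visit 12 from 2 to 3 weeks so that it matches the control instruction, and check that the Visit 11, Visit 12, Visits 13 to 15 and Visit 16 text and any logbook instructions then agree. In the analysis of log-based events, use days actually logged as the exposure (an offset in the Poisson or negative binomial model) instead of a fixed 21 days. For this to work, the logbook must distinguish a day without events from a day not recorded.

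The cost is a one-word amendment and an offset term. No visit, procedure or treatment changes. The wording should be corrected before participants reach Visit 12; for any who have already passed it, the days-logged exposure is the available remedy, as far as the logbooks show which days were kept.
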